2. INTRODUCTION

This Statistical Analysis Plan (SAP) defines the statistical methods and data presentations to be used by CELLTRION Clinical Statistics team in the analysis and presentation of data from CELLTRION study number CT-P10 3.4, entitled as “A Phase 3, Randomised, Parallel-Group, Active-Controlled, Double-Blind Study to Compare Efficacy and Safety between CT-P10 and Rituxan in Patients with Low Tumour Burden Follicular Lymphoma”.

There are two clinical study reports (CSRs) planned for the following time points, with provision of additional CSRs if required for regulatory or academic purposes:

- After all eligible patients have completed the 7 month assessment (prior to Cycle 3 of the Maintenance Study Period)
- After all patients have completed or terminated from the study

This SAP covers full study analyses and data presentation and is based on the following documents:

- Study Protocol Version 4.0 – 28th June 2017
- Unique Case Report Form Version 6.0 – 7th July 2017

Table, Listing and Figure (TLF) mock shells will be provided as an addendum to this document.

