10.1.1. Overall Response Rate

Overall response rate (ORR) is defined as the proportion of patients whose BOR is CR, CRu or PR (the ‘responders’). For the primary analysis, the BOR will be derived from the overall responses according to the Modified Response Criteria for Malignant Lymphoma across all time points up to 7 months assessment (Prior to Cycle 3 of the Maintenance Study Period). When CR, CRu, PR or SD is believed to be the best response, it must also meet the minimum 8 weeks from randomization. If the minimum duration is not met in case of CR, CRu, PR or SD, the patient’s BOR will be decided as the best response among subsequent assessments fulfilled the minimum

duration. For example, a patient who has SD at first assessment, progressive disease at second and does not meet minimum duration for SD, will have a best response of progressive disease. If the patient lost to follow-up after the first SD assessment, the patient's overall response would be considered to be unevaluable. In the case when a patient has an assessment result of PD within the minimum duration of 8 weeks from randomization, the patient's BOR will be considered as PD.

ORR up to 7 months will be compared between CT-P10 group and Rituxan group for the ITT population and PP population. A point estimate and 90% CI of the difference between two proportions will be presented using an exact binomial method. Similarity will be demonstrated if the two-sided 90% CI for the difference in proportion between CT-P10 and Rituxan is within the equivalence margin of $\pm 17\%$. Additional exact binomial test will be conducted for ITT population – ADA Negative/Positive subset and PP population – ADA Negative/Positive subset. If the number of ADA Positive subset is very small ($\leq 5\%$ of ITT population or PP population) then the subset will not be summarized since it is not statistically meaningful.

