10.1.2. Sensitivity Analysis

As the exact binomial method does not allow for stratification, a sensitivity analysis will be performed on the primary efficacy endpoint, utilizing a logistic regression model with treatment as a fixed effect and region (Asia Pacific vs. Europe vs. North America and Other), Ann Arbor stage (Lower than or equal to II vs. III vs. IV) and age (≥ 60 vs. < 60 years) as covariates. The resulting odds ratio and 90% CI will be converted into difference of proportions using the Delta method for the purpose of comparison of proportions. The sensitivity analysis will be conducted in the ITT population and the PP population supportively.

Difference of proportions using the Delta method is explained in the following process.

- 1) The individual odds and standard errors (SEs) for both treatments will be obtained from the model. For the purposes of this algorithm, let the estimate of the odds of being a responder in the CT-P10 group be denoted by θ_a and the estimate of the odds of being a

responder in the Rituxan group be denoted by θ_b

- 2) Calculate the variances of these estimates, $\text{Var}(\theta_a)$ and $\text{Var}(\theta_b)$ respectively from the SEs obtained from the model.
- 3) Calculate the estimates of the corresponding proportions, denote p_a and p_b respectively, for each of the treatment groups, from the estimated odds using the following formula:

$$p_a = \frac{\theta_a}{1 + \theta_a}, \quad p_b = \frac{\theta_b}{1 + \theta_b}$$

And hence calculate the estimate of the difference of proportions ($p_a - p_b$).

- 4) Using Taylor expansions and the Delta method, the following formula for approximation can be obtained:

$$\text{Var}[f(X)] \approx (f'(E[X]))^2 \text{Var}[X]$$

Applying this approximation specifically to this case, and using the formula specified in step (3) we obtain the formula

$$\text{Var}(p_a) = \frac{\text{Var}(\theta_a)}{(1 + \theta_a)^4}, \quad \text{Var}(p_b) = \frac{\text{Var}(\theta_b)}{(1 + \theta_b)^4}$$

Which should be used to calculate $\text{Var}(p_a)$ and $\text{Var}(p_b)$.

- 5) Calculate the variance of the difference in proportions $\text{Var}(p_a - p_b)$ as the sum of $\text{Var}(p_a)$ and $\text{Var}(p_b)$. Use this to obtain the SE of the difference, and hence calculate the 90% CI using the formula:

$$90\% \text{ Confidence Interval} = (p_a - p_b) \pm 1.64 [\text{SE}(p_a - p_b)]$$

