Note: this method assumes that the estimate ORR of CT-P10 group is independent of the estimate ORR of the Rituxan group.

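### The logistic sensitivity analysis takes both arms' response rates from one model but adds their variances as if independent, so at a fixed covariate setting its 90% CI is generally too wide (supportive analysis, low severity)

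*SAP*

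**What the plan says.** SAP 10.1.2 presents the analysis as the answer to the exact method's inability to stratify, "utilizing a logistic regression model with treatment as a fixed effect and region", Ann Arbor stage and age as covariates. In outline: "The resulting odds ratio and 90% CI will be converted into difference of proportions using the Delta method".

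The five steps that follow work differently from that outline. Step 1 reads: "The individual odds and standard errors (SEs) for both treatments will be obtained from the model". Step 2 squares the standard errors. Step 3 forms a proportion "for each of the treatment groups, from the estimated odds using the following formula", p = θ/(1+θ). Step 4 gives Var(p) = Var(θ)/(1+θ)^4. Step 5 begins "Calculate the variance of the difference in proportions" and defines it as the sum of the two variances; the interval is the difference ± 1.64 SE. A closing note states the premise: "this method assumes that the estimate ORR of CT-P10 group is independent of the estimate ORR of the Rituxan group".

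The section does not say at which covariate values the odds are evaluated. Two places outside it might. The software names in SAP 5.1 are redacted, and SAP 2 says: "Table, Listing and Figure (TLF) mock shells will be provided as an addendum to this document".

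The decision rule sits elsewhere, in SAP 10.1.1, and refers to the exact binomial interval: "Similarity will be demonstrated if the two-sided 90% CI for the difference in proportion between CT-P10 and Rituxan is within the equivalence margin" of ±17%.

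**The concern.** Independence would hold if each arm's rate came from that arm's data alone. Here both come from one fit. The two linear predictors differ only in the treatment coefficient and share the intercept and five covariate coefficients (two each for region and stage, one for age). At a common covariate setting their errors are therefore generally positively correlated, and step 5 drops the term 2Cov(pa, pb). Stating the assumption does not make it true, and the fitted model already supplies the missing term. The model's own odds-ratio CI, which the outline says is converted, contains that covariance; the five steps discard it.

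At stake is the correctness and reproducibility of the only covariate-adjusted analysis of the primary endpoint. An interval that is too wide could put the supportive result outside ±17% without cause. If no setting is fixed anywhere, two programmers could report different estimates and intervals from the same fit.

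**Working it through.** **Inputs from the SAP.** 87 per arm, ORR 88% in both arms, margin ±17 points, two-sided 90% CI, 13% drop-out for the PP population (SAP 5.2); model terms and multiplier 1.64 (SAP 10.1.2).

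**Inputs assumed.** The documents give no stratum shares or covariate effects. I took six share mixes and three effect sets. Effects are log odds ratios for the second and third levels against the first: none; moderate (region 0.3, -0.3; stage -0.3, -0.6; age -0.4); strong (region 0.8, -0.8; stage -0.8, -1.5; age -1.0).

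**The plan's own figures.** It states no figure for this interval, but its power reproduces. Full binomial enumeration of two one-sided 5% tests at 87 per arm gives 90.8% (exact) and 91.1% (score) against the stated 91%. At 76 per arm (174 × 0.87 / 2 = 75.7) it gives 85.1% and 86.6% against 86%.

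**Step 4 is sound.** With θ = exp(x'β), Var(θ) = θ² x'Vx, so Var(p) = [p(1-p)]² x'Vx. This is the correct delta-method variance for one arm.

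**Step 5 is not.** Var(pa - pb) = Var(pa) + Var(pb) - 2Cov(pa, pb), where Cov(pa, pb) = pa(1-pa) × pb(1-pb) × xa'V xb.

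**Closed form** (balanced arms, independent factors, no covariate effects): step-5 SE / correct SE = sqrt(1 + q/2), with q = sum over factors of [sum_k c_k²/s_k - 1], c_k the weight at the chosen setting and s_k the stratum share.

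- Correct SE = sqrt(2 × 0.88 × 0.12 / 87) = 0.0493; half-width 1.64 × 0.0493 = 8.1 points.
- Observed means: c = s, q = 0, ratio 1.00.
- Equal weights, region 60/25/15, stage 15/35/50, age 45/55: q = 0.370 + 0.280 + 0.010 = 0.661; ratio sqrt(1.330) = 1.153; half-width 9.3 points.
- Equal weights, region 12/76/12, stage 20/40/40, age 50/50: q = 0.998 + 0.111 + 0 = 1.109; ratio 1.247; half-width 10.1 points.
- Equal weights, region 5/85/10, stage 10/40/50, age 40/60: q = 2.464 + 0.611 + 0.042 = 3.117; ratio 1.600; half-width 12.9 points.

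**With covariate effects.** The same ratio from the expected logistic information matrix, as SE excess for no / moderate / strong effects:

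| Shares (region; stage; age) | Observed means | Equal weights |
|---|---|---|
| all equal | 0 / 2 / 14% | 0 / 2 / 14% |
| 45/35/20; 20/40/40; 50/50 | 0 / 2 / 12% | 6 / 9 / 22% |
| 60/25/15; 15/35/50; 45/55 | 0 / 2 / 11% | 15 / 22 / 42% |
| 12/76/12; 20/40/40; 50/50 | 0 / 2 / 11% | 25 / 21 / 24% |
| 10/80/10; 20/35/45; 50/50 | 0 / 2 / 11% | 32 / 27 / 29% |
| 5/85/10; 10/40/50; 40/60 | 0 / 2 / 9% | 60 / 58 / 68% |

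If predictions are averaged over patients in each arm's scenario, the ratio is 1.000 in every row.

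**Finite samples.** In simulated trials of 174 patients (first three mixes, no or moderate effects, permuted blocks of 4 assumed), the median excess was 3-6% at observed means, 4-26% at equal weights and 0% when standardised. Between 0.5% and 14.7% of fits did not converge and were dropped, so these medians describe fitted trials only.

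**Consequence.** On a normal approximation with no true difference and no covariate effects, the chance that the interval lies inside ±17 points is 2Φ((17 - half-width)/4.93) - 1. This is 93% at ratio 1.00, 84% at 1.25 and 59% at 1.60.

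**The case against.** The strongest reply is that little harm is shown where the SAP is read most naturally.

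- **Size.** At observed means with weak to moderate effects the excess is a few per cent. If the programmer averages over patients, the covariance is about zero and the note, which speaks of each group's ORR, is nearly right. This stands, and it is why the severity is low.
- **The remedy may not shorten the interval.** In the simulated trials of 174, the median half-width was 7.7-7.9 points for step 5 at observed means against 7.9-8.0 for the standardised interval, and step 5 was the narrower in 82-87% of fits. This also stands: too wide means too wide for the quantity estimated at that setting.
- **The setting may be specified elsewhere.** The software is redacted and the output shells are a separate addendum. So one can say only that the visible text does not fix it, not that the plan fails to.
- **The assumption is disclosed, and the analysis is supportive.** Both are true. Disclosure does not repair a premise that the specified model contradicts, but SAP 10.1.2 attaches no decision rule to this interval.
- **The mismatch between converting the odds ratio and using separate arm odds is only wording.** Largely so, since the steps are offered as the explanation of that conversion.

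A reader might go further and infer a raised risk of false similarity from evaluating both arms at one reference patient profile. The documents do not support that. A single profile fits the SAP's reference to each treatment group poorly, and any such effect would come from the choice of profile, not from the summed variance.

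**Conclusion.** The independence premise generally fails for the model that SAP 10.1.2 specifies, and at a fixed covariate setting the step-5 standard error is generally too large. The algebra does not depend on assumptions; the size does.

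Under the assumed shares and effects, the excess at observed means is negligible only if covariate effects are weak to moderate; strong effects take it to 9-14%. At equal weights about a quarter is not a ceiling. It covers balanced to moderately unequal strata with no or moderate effects. Two regions of 10% each give about 30%, and a very small stratum, or unequal strata with strong effects, gives about 40-70%.

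Two stronger inferences should be resisted. First, this does not touch the trial's similarity claim: the exact binomial CI, its error rate, the ±17% rule and the sample size are all unaffected. Second, excess width at one setting does not guarantee conservatism for the overall ORR difference, because the setting also changes the estimated difference. The point is a low-severity error in a supportive analysis, worth correcting because correction is nearly free.

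**What to change.** **Minimum.** In step 5 use the full model covariance matrix V: Var(pa - pb) = g'Vg, with g the gradient of pa - pb. Equivalently, subtract 2Cov(pa, pb) using the expression under the working. State in SAP 10.1.2 the covariate values or weights at which the arm odds are evaluated, or cite where they are given. Delete the independence note.

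**Preferred.** Report the standardised risk difference from the same model: the mean predicted response with all patients set to CT-P10 minus the mean with all set to Rituxan, with delta-method variance g'Vg. This removes the choice of setting and estimates a difference averaged over the trial's own patients. The aim is a correct and reproducible interval, not a narrower one.

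**Cost.** SAP wording and a few lines of code. No new data and no change to the primary analysis.

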10.2. Secondary Efficacy Endpoint

The following efficacy parameters for the study drug will be analyzed as secondary endpoints:

- Overall response rate (CR + CRu + PR) during the study period according to the Modified Response Criteria for Malignant Lymphoma

- Progression-free survival, defined as the interval between randomization and disease progression/relapse, or death from any cause, whichever occurs first
- Time to progression, defined as the interval between randomization and disease progression/relapse or death as a result of lymphoma, whichever occurs first
- Overall survival, defined as the interval between randomization and death from any cause

All time-to-event analyses excluding overall survival will be performed only for the final CSR for the central (up to MP2) and local (up to Follow-up) review. Time to overall survival analysis will be only conducted in the local review in the final CSR. Records on ‘Survival Status’, ‘Response Evaluation’ or ‘Study Treatment Termination’ eCRF page will be used.

For the Progression-free survival, Time to Progression and Overall Survival, the number of patients with events and censoring will be summarized on the ITT population. The reasons for events or censoring will be also presented on the table. The 25th percentile, 50th percentile (median) and 75th percentile of each time-to-event parameter and 95% CI for each treatment group will be displayed using the Kaplan-Meier method. The survival rates per 6 months will be estimated by the Kaplan-Meier method and presented along with their corresponding 95% CI. A Kaplan-Meier curve will also be provided for each the time-to-event analyses for the ITT population.

Descriptive Statistics including the 25th percentile and 75th percentile of Follow-up Duration will be provided for the ITT population.

Time-to-event analyses, event or censoring information (e.g., Date of Event, Reason for Event) will be listed by treatment group for the ITT population.

All secondary efficacy endpoint analyses will be conducted only for final CSR.

10.2.1. Overall Response Rate

For the secondary efficacy endpoint, the ORR during the study period (Overall and up to MP1) according to Modified Response Criteria for Malignant Lymphoma will be analyzed.

ORR during study period and the number and percentage of patients within each response category will be summarized by treatment group for the ITT population and the PP population. The table will be generated twice by using data from the central review and the local review.

Moreover, ORR and the number and percentage of patients will be summarized by visit for the ITT population and PP population. The table will be also generated twice by using data from the central and local review.

10.2.2. Progression-Free Survival

Progression-free survival (PFS) is defined as the interval between randomization and disease progression/relapse or death from any cause, whichever occurs first (Cheson et al 2007).

Censoring will be defined as following:

Reason for Censoring	Censoring date
No tumour assessments	Randomization date
Ongoing without event	Last tumour assessment date
Study termination for any reason without documented progression/relapse or death	Last tumour assessment date before study termination
New anticancer treatment started	Last tumour assessment date before salvage treatment
Death or progression after more than one missed visit ¹	Last tumour assessment date if there are missing visits before PD or death

¹ If there is only one missed visit, then it will be considered as an event case. Otherwise, it will be considered as a censoring case.

Time-to-event for PFS will be calculated as follows:

$$\text{Time-to-event for PFS (Months)} = (\text{Date of Event/Censoring} - \text{Date of Randomization} + 1) / 30.4$$

10.2.3. Time to Progression

Time to progression (TTP) is defined as the interval between randomization and disease progression/relapse or death as a result of lymphoma, whichever occurs first (Cheson et al 2007).

Censoring will be defined as following:

Reason for Censoring	Censoring date
No tumour assessments	Randomization date
Ongoing without event	Last tumour assessment date
Study termination for any reason without documented progression/relapse or death	Last tumour assessment date before study termination
New anticancer treatment started	Last tumour assessment date before salvage treatment
Death due to lymphoma or progression after more than one missed visit ¹	Last tumour assessment date if there are missing visits before PD or death
Death due to reason other than lymphoma	Last tumour assessment date before death due to reason other than lymphoma

¹ If there is one missed visit, then it will be considered as an event case. Otherwise, it will be considered as a censoring case.

Time-to-event for TTP is calculated as follows:

Time-to-event for TTP (Months) = (Date of Event/Censoring – Date of Randomization + 1) / 30.4

10.2.4. Overall Survival

Overall survival (OS) is defined as the interval between randomization and death from any cause (Cheson et al 2007). For patients whose status with no death recorded or lost to follow-up, data will be censored at the time when the patient was last known to be alive.

Time-to-event for OS is formulated as follows:

Time-to-event for OS (Months) = (Date of Event/Censoring – Date of Randomization + 1) / 30.4

10.2.5. Follow-up Duration

Follow-up duration is defined as the interval between randomization date and last information date. Event in the following order (No censored cases):

- 1) Patient withdrew consent
- 2) Patient lost to follow-up
- 3) Death
- 4) Study is closed
- 5) Other

Follow-up duration is formulated as follows:

Follow-up duration (Months) = (Date of Event – Date of Randomization + 1) / 30.4

10.3. Bone Marrow

Bone marrow testing will be done according to [APPENDIX 1](#).

The number and percentage of patients with each bone marrow assessment result will be tabulated by treatment group and visit for the ITT population. The results will be listed by treatment group for ITT population including PP population flag.

10.4. B-symptoms

B-symptoms in lymphoma patients are disease-related clinical symptoms that are not caused by

anticancer therapy (or drug toxicity), and are defined as follows:

- Significant unexpected fever (>38 °C)
- Unexplained, recurrent drenching night sweats
- Unexplained loss of more than 10% of body weight within the previous 6 months, as assessed and reported (present versus absent) by the investigator.

The number and percentage of patients with at least one B-symptom and patients per symptom will be tabulated by treatment group and visit for the ITT population. The results will be listed by treatment group for ITT population including PP population flag.

10.5. β -2 microglobulin

Blood samples for β -2 microglobulin will be assessed at the time points specified in [APPENDIX 1](#).

The number and percentages with β -2 microglobulin results will be presented by treatment group and visit for the ITT population. All β -2 microglobulin data will be listed by treatment group and visit.

11. PHARMACOKINETIC ANALYSES

All pharmacokinetic analysis will be performed on the PK population unless otherwise specified. Blood samples for pharmacokinetic analysis will be obtained according to [APPENDIX 1](#).

11.1. Serum concentrations

Serum concentrations of rituximab will be summarized using descriptive statistics by treatment group at each scheduled collection time for PK population. Serum concentrations below the lower limit of quantification (BLQ) at baseline (predose at Induction Study Cycle 1) will be set as zero. Serum concentrations BLQ after study drug exposure will be set as the lower limit of quantification (LLOQ). Descriptive statistics will consist of n, mean, standard deviation, geometric mean, CV%, minimum, median and maximum. Geometric mean will not be reported if the dataset includes zero values, CV% will not be reported if the mean is zero.

Mean serum concentration-time profiles of rituximab will be plotted by treatment on linear and semi-logarithmic scales based on scheduled sample times for PK population. Individual linear

concentration-time plots based on scheduled time by treatment group will also be conducted for PK population.

Serum concentrations of rituximab will be presented for the Safety population by treatment in a listing.

11.2. Pharmacokinetic Parameters

The secondary pharmacokinetic endpoints are Maximum serum concentration (C_{max}) and Trough serum concentration (C_{trough}) at each dose. C_{max} is the observed maximum serum concentration following drug administration, and C_{trough} is the observed trough serum concentration following drug administration; calculated from the predose concentration of the next dose. If the patient discontinued before next dose, concentration at EOT1 (for Cycles 1 to 3 in Induction Study Period) or EOT2 (for Cycle 4 in the Induction Study Period where there is no predose for Cycle 1 Maintenance) will be used. Serum concentrations BLQ at baseline (predose at Induction Study Cycle 1) will be set as zero. Serum concentrations BLQ after study drug exposure will be set as LLoQ. Missing values for any PK parameters will not be imputed.

The table will summarize the PK parameters using descriptive statistics by treatment group: n, mean, standard deviation, geometric mean, CV%, minimum, median and maximum. Geometric mean will not be reported if the dataset includes zero values, CV% will not be reported if the mean is zero.

Pharmacokinetic parameters for the PK population will be listed.

